Each testing session will be separated by at least two days. Subjects will be instructed to perform a precision grip (between index and thumb) and simultaneously wrist flexion or extension movements. Measurements of cortical and motoneuronal excitability will be acquired during movement. Tasks involving lower-limb movement will also be tested as control tasks. In each session, we will use the following experimental setup and motor tasks:

Experimental setup – During testing, individuals will be seated in an armchair with both elbows flexed at 90°. Each arm will be supported by a custom device attached to a potentiometer to measure wrist flexion and extension angles and a load cell to measure grip forces. Index fingers and thumbs will be positioned in a customized gripping tube attached to a two-axis load cell. Subjects who cannot be transferred will be tested in their wheelchair by using customized platforms that we previously used in individuals with SCI. Surface electrodes will be positioned bilaterally on the skin overlying upper and lower-limb muscles in a bipolar montage (inter-electrode distance approximately 2 cm). The amplified EMG signals will be filtered, sampled, and stored for analysis. Forces will be measured by load cells and angles by potentiometers and stored for analysis.

Motor task – In a first test, subjects will be instructed to perform full wrist flexion and simultaneously perform a precision grip (between index and thumb) with one hand. In a second test, subjects will be instructed to perform full wrist extension and a precision grip with one hand. At the start of testing,

individuals will perform 3 brief precision grip maximum voluntary contractions (MVCs) (3–5 s) and wrist flexion and extension MVC with 30 seconds of rest. Custom software will be used to acquire signals from potentiometers and load cells to display visual feedback corresponding to wrist flexion and extension angles and 10% of MVC grip force. Subjects will be instructed to move a cursor at a comfortable speed and to hold the cursor in the target force and position for 2-4 seconds. During lower-limb tasks subjects will be instructed to move as cursor by performing ankle dorsiflexion and plantar flexion movements. Approximately thirty repetitions of each task will be randomly tested.

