Lower Extremity Physiological Examination Components:

Range of Motion (ROM): active ankle and hip ROM will be measured by a motion capture system (Opti Track, V120: Tri camera, NaturalPoint, Inc) in sitting and standing position. In sitting, subjects will be instructed to complete maximal voluntary dorsiflexion for 10 times separated for period of 10 sec of rest. In standing, subjects will be instructed to complete maximal voluntary hip flexion for 10 times separated for period of 10 sec of rest. Trunk movements will be avoided during testing. The motion capture system will also be utilized to measure foot drop and hip flexion. Markers will be positioned on the external line of the mid trunk, hip, knee, external malleolus, and the lateral side of the 5th metatarsophalangeal joint. The elevation of the toe above ground level will be taken as a measure of foot drop. The amplitude of toe elevation will be calculated from the distance between the marker placed on the 5th metatarsophalangeal joint and the ground (Barthélémy et al., 2010). The largest distance between these two points will be determined and will be referred to as the highest toe elevation. The presence or absence of the second toe elevation prior to heel strike will be measured by subtracting the excursion of the malleolus marker from the elevation of the toe. Hip angle will be constructed by using the trunk, hip and knee markers.

Pinch Grip Strength:

Will be assessed bilaterally using load cells that will record the force generated by the subject. Force will be applied by the thumb and index finger and will be recorded in Newtons (N).

Modified Ashworth Scale and Pendulum Test:

Will be used to measure spasticity level in subjects with SCI during soft tissue stretching.
(Modified Ashworth Scale; Bohannon and Smith, 1987)

Phase 3

Experiment 2 (Aim 2b) :

Individuals with SCI and healthy controls will be randomly assigned to two groups: (1) training + rTMS, and (2) training + sham rTMS. Randomization will be the same as described above. Training will be complete in approximately 15 sessions over approximately 3 weeks. In each session, stimulation or sham stimulation (approximately 25 minutes) will be applied during precision grip and wrist visuo-motor training (approximately 1 hour).

Training + rTMS group- Training will consist of executing three different grip forces with one hand and simultaneously wrist flexion and extension movements while the contralateral hand is at rest.

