Subjects will be instructed to follow a target line on a computer screen as accurately as possible while performing precision grips with simultaneously maximal wrist flexion and extension. Stimulation will be triggered if both movements are performed. See Experiment 1 for rTMS parameters. At each time three targets will be presented separated by approximately 2 seconds of reset on the screen for a total duration of 10 seconds. The period of stimulation will last approximately 24 minutes. Subjects will be randomly assigned to two groups: training + rTMS, and training + sham rTMS. A train of rTMS will be applied during each of the target presentations. The coil will be positioned over the optimal scalp position for activating finger and wrist muscles. Here, 5 pulses at 5 hz will be applied each time that a target appears on the computer screen. In a control task individuals will be asked to perform to follow the same cursor using their lower limb muscles. A total of 1200 rTMS pulses will be applied at 80% of AMT intensity (see more details about rTMS application in AIM 2a).

Training+sham rTMS group- Training will be conducted as described above. For sham rTMS, TMS coil will be positioned in the same location as described above. A second coil will be placed behind the subjects head, and it will discharge in the air using the same stimulation parameters that will be used in the TMS application. During sham stimulation only the coil located behind the subjects head will be triggered. Participants may feel small pressure from the coil positioned on top of their head and hear the click sound during triggering.

Measurements before and after rTMS protocols:

Physiology- We will examine: (a) MEPs, SICI, IHI, and F-wave (See procedures in Aim 1). Precision grip motor performance: We will quantify the following outcomes: (a) Force onset [the time point at which force increases 2SD above force baseline], (b) Force rate (maximum derivative of force (force/s) between force onset and target force), (c) Force area (area between force onset and force decay to zero), and (d) Total force duration (time between force onset and force decay to zero).

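### Aim 2b trains accurate following of a target line, but none of its four precision-grip outcomes measures deviation from target, and force area and duration have no fixed direction of benefit.

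*Combined protocol and SAP*

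**What the plan says.** Under Phase 3, Experiment 2 (Aim 2b), stimulation or sham "will be applied during precision grip and wrist visuo-motor training". Training consists of "executing three different grip forces with one hand and simultaneously wrist flexion and extension movements", and the instruction is "Subjects will be instructed to follow a target line on a computer screen as accurately as possible while performing precision grips". The wrist part is described as "precision grips with simultaneously maximal wrist flexion and extension".

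The section on measurements before and after the rTMS protocols lists four precision-grip performance outcomes:

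- force onset, when force exceeds baseline by 2 SD;
- force rate, the steepest rise between onset and target force;
- "c) Force area (area between force onset and force decay to zero";
- "Total force duration (time between force onset and force decay to zero".

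The Phase 3 follow-up section names the same four for months 1, 2 and 3. Section G tests group and time effects on physiological outcomes and motor performance. It singles out no performance measure and gives no direction of benefit. The study's primary outcomes, under Methodology, are muscle responses to TMS and to peripheral nerve stimulation.

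**The concern.** The Aim 2b hypothesis is that rTMS enhances the outcomes of precision grip training. The instruction makes accuracy the goal of that training, so a reader expects at least one outcome that compares produced force with the target. There is none. Two of the four measures, area and duration, can move either way when accuracy gets worse. A group difference in either one, taken alone, therefore cannot be read as better or worse performance.

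The end rule adds a separate problem. Onset is set relative to a measured baseline, which allows for a baseline other than zero, while the end of the grip requires zero.

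At stake is whether the behavioural part of Aim 2b can show a gain or loss in the skill that was practised.

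**Working it through.** The plan gives no figure to reproduce. The check has three steps.

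**1. Definitions against the instruction.**

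| Outcome | Uses the target? | Is a deviation from target? |
|---|---|---|
| Force onset | No | No |
| Force rate | Only as the end of its interval | No |
| Force area | No | No |
| Total duration | No | No |

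So 0 of 4 measure accuracy. The other Aim 2b measures do not fill the gap. The Jebsen Taylor test, Chedoke inventory, pinch force, SCIM self-care and CUE assess function or strength. ASIA and EPT assess sensation. The only range-of-motion procedure described is "active ankle and hip ROM will be measured by a motion capture system". Aim 2a computes a mean force plus 1 SD, but that value sets the later visual feedback and is not an Aim 2b error score.

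**2. Direction of area and duration.** The following inputs are assumptions, not protocol values:

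- The target is 10 units, shown from 0.5 s to 2.5 s. Two seconds per target is consistent with Aim 2b's three targets about 2 s apart within 10 s: (10 − 2 × 2)/3 = 2.
- Force starts at 0.45 s and rises at 50 units/s.
- RMS error is taken over 5 s, so it includes the time after the target ends.

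For a trace with peak P, rise time r, hold h and fall time f, area = P × (r/2 + h + f/2). Duration is counted while force exceeds 0.2 units.

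| Trace | P, r, h, f | Area | Duration (s) | RMS error |
|---|---|---|---|---|
| Accurate | 10, 0.20, 1.80, 0.2 | 20.0 | 2.19 | 1.08 |
| 50% overshoot | 15, 0.30, 1.70, 0.2 | 29.25 | 2.19 | 3.26 |
| Slow release | 10, 0.20, 1.80, 1.2 | 25.0 | 3.17 | 2.76 |
| Both faults | 15, 0.30, 1.70, 1.2 | 36.75 | 3.18 | 5.03 |
| 30% undershoot | 7, 0.14, 1.86, 0.2 | 14.2 | 2.19 | 2.08 |
| Early release | 10, 0.20, 1.00, 0.2 | 12.0 | 1.39 | 3.86 |

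Every faulty trace has more error than the accurate one. Relative to the accurate trace:

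- Area rises by 25% (25/20), 46% (29.25/20) and 84% (36.75/20) in the first three faults. It falls by 29% (14.2/20) and 40% (12/20) in the last two.
- Duration rises by 45% with slow release (3.17/2.19) and falls by 37% with early release (1.39/2.19). It does not change with overshoot or undershoot alone.

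Onset and rate are the same in all six traces because they were set so. That is an input, not a finding.

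**3. The end rule.** If force settles at a resting level R above zero, decay to zero is not reached before the next grip. Over a gap of G seconds, duration then gains G and area gains about R × G, however small R is. The Aim 2b targets are about 2 s apart, so up to about 2 s could be added to a grip that lasts 2.19 s in the illustration. If no zero occurs in the record, both measures are undefined. If the load cell is zeroed and resting force is zero, the rule works.

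**The case against.** The strongest reply is that the outcomes should be read together. Constant overshoot raises area with duration unchanged, so area divided by duration exposes it. Undershoot held for longer leaves area unchanged but lengthens duration: for a 10-unit target, 8 × 3.75 = 30 = 10 × 3, with duration up 25% (3.75/3). That stands, and it is why the point is limited to each measure read alone. It does not replace an error score, because the plan specifies no joint reading. Nor would the pair detect error that cancels within a hold: 1 s at 12 units and 1 s at 8 gives 12 + 8 = 20, the same as 10 × 2, with force 20% off target throughout.

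A second reply is that trials may reasonably assess function instead of the practised task, and Aim 2b has several functional tests. That is fair, and it limits the importance. The plan nevertheless chose to list grip-performance outcomes, and these do not score what participants were told to do.

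Four stronger readings are tempting, and the documents do not support them:

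- **That wrist-angle tracking is trained and left unscored.** The wrist movement is described as maximal and Aim 2b states no wrist target. The cursor display of wrist angle belongs to Aim 1.
- **That the plan would call a rise in area or duration an enhancement.** It states no direction for either.
- **That the end rule produces error related to spasticity, or bias between arms.** The documents give no resting-force data and no zeroing rule, and the rule applies to both randomised groups.
- **That the primary analysis is compromised.** The primary outcomes are evoked responses.

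**Conclusion.** The concern holds in this limited form. None of the four grip-performance outcomes measures deviation from target, although accuracy is the explicit training instruction. Area and duration cannot be read singly as better or worse performance. The end rule fails whenever resting force is above zero; how often that happens is unknown from the documents.

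The percentages depend on the assumed traces. Only the qualitative result is general: area and duration can rise or fall as error rises. Aim 2b does not give its three force levels, and area scales with the level with no normalisation stated. The change should be made, but the effect is confined to the secondary, behavioural test of Aim 2b.

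**What to change.** 1. Add a target-referenced force error as an Aim 2b grip-performance outcome. One form is the RMS or mean absolute deviation from target force over the target period, as a percentage of target, with lower stated as better. Fix the window in advance. In the illustration, error restricted to the 2 s target period is 1.19 for slow release against 1.21 for the accurate trace, so a window that stops with the target misses slow release. If release matters, extend the window into the following rest.
2. End each grip when force falls below the same baseline plus 2 SD level that defines onset.
3. Report area and duration as descriptive, with neither a rise nor a fall claimed as improvement.
4. Optionally, report attained wrist angle if it is recorded in Aim 2b. Do not specify a wrist tracking error, since no wrist target is stated.

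The cost is low. Force rate already needs a recorded force trace and a known target force. The Aim 1 apparatus stores both signals ("Forces will be measured by load cells and angles by potentiometers and stored for analysis"), though Aim 2b does not restate that setup and should confirm it. No added participant testing is needed. The downside is one more derived outcome in a secondary family.

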(B). Motoneuronal excitability (reflected by F-wave persistence and amplitude): F-waves will be tested by using supra-maximum stimulus intensity (120% of the maximal motor response) to the ulnar nerve at the wrist and the median nerve at the elbow. The anode and cathode will be approximately 3 cm apart and 1 cm in diameter. We will examine F-waves in first dorsal interosseous, flexor and extensor carpis radialis muscles.

Phase 2

Aim 2a. Enhance recovery of motor function by using non-invasive repetitive transcranial magnetic stimulation (rTMS)

To accomplish this aim we propose to complete two main experiments. First we will use rTMS to test the hypothesis that *rTMS induced cortical plasticity during movement will enhance voluntary output in hand muscles (as measures by electromyography and Jebsen Taylor Test) after spinal cord injury (Aim 2a)*. Second, we will combine precision grip and wrist training with rTMS to test the hypothesis that *precision grip training outcomes will be enhanced by rTMS induced cortical plasticity (aim 2b)*.

Experiment 1 (Aim 2a)

Participants will be randomly assigned to three groups: (1) rTMS, (2) Sham rTMS and (3) sham rTMS over control brain area. Randomization will be performed by lottery (i.e. Drawing from an envelope a piece of paper indicating the intervention). In the first two groups, rTMS stimulation will be targeting finger and wrist muscles during precision grip and write voluntary contractions. In the last group, rTMS will be applied over the dorsolateral prefrontal cortex (DLPFC) or at the leg presentation of the primary motor cortex, or at other related control area as needed. Each subject will be asked to participate in all sessions separated by a washout period of approximately one week. During testing, subjects will be seated in an armchair with both arms flexed at the elbow by 90 degrees. In each group we will use the same apparatus described in Aim1. At the start of the experiment subjects will perform 3 brief MVCs (3-5s) into index finger abduction and wrists flexion and extension, separated by 30 seconds. The maximal forces will be used to set targets for subsequent submaximal contractions.

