Motor function- We will use range of motion (ROM), JTT, Pinch force, Chedoke arm and Hand inventory, and sensory function of the upper and lower extremities using the American Spinal Injury Association (ASIA) sensory scores and Electrical Perceptual Threshold (EPT). These functional and sensory tests are described in detail in Aim 2a.

Plan for multiple rTMS sessions using Brainsight for MRI co-registration: to ensure that the same area of the motor cortex is stimulated during multiple rTMS sessions we will use the Brainsight co-registration system. We will use an MRI scanner located at the University of Miami Applebaum MRI center or at the Miami VA Medical center. Individuals will be asked to participate in the scan session at their convenience as soon as they are enrolled in Aim 1 of this proposal. Individuals who only participate in Aim 2 of the study will be asked to have the MRI session after they have signed the consent form.

Plan for assessment of long-term effects of rTMS: Physiological and behavioral measurements will be acquired before and after sessions 1,5, and 10.

Phase 3- Follow up

Follow up measurements will be taken after 1, 2, and 3 months after Phase 3 testing to measure any sustained improvements in hand function. This assessment will be completed in a single session. These assessments will be the same as in Phase 1-3 of this research study. Each session will last about 1 hour.

Physiological measurements- We will examine MEPs, SICI, IHI, and F-waves (see procedures in Aim1). Precision Grip motor performance: we will examine Force onset, rate, area and total force duration (see procedures in Aim 2a.) Hand motor function: we will examine JTT, Pinch force, Chedoke Arm and Hand inventory, and sensory function of the hand using the American Spinal Injury Association (ASIA) sensory scores (see procedures in Aim 2a).

Assessment of quality of life and functional independence after SCI- the following measurements will be conducted before and after training sessions in Aim 2B, and at the follow up visits 1,2, and 3 months after training.

- (a) Self-care subscale of the spinal cord independence measure- Version III (SCIM; itzkovich et al., 2007)
- (b) The Capabilities of upper Extremities (CUE; Marino et al., 1998)

Demographics will be collected in all subjects. This will include variables such as age, gender, race, height, weight, and veteran status. For individuals with SCI, we will also collect level of injury and date of injury.

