Screening Interview: Identifiable information collected during either the screening interview will be destroyed if the potential subject does not qualify. If the subject does qualify and ultimately enrolls into this research, all information collected will become part of their research record. All security precautions that are reflected in this protocol will apply.

Data Collection and Storage: Research records will be retained in accordance with the Veterans Health Administration (VHA) Records Control Schedule. The Federal Privacy Act protects the confidentiality of medical records. Electronically-stored medical information collected from study participants will be kept on a VA server. Electronic data recorded during experimental sessions will be kept on fully-secured computers (password protected) on a VA server. Unique subject identifiers (i.e., a code accessible only to the PI and AI) will be used to label all electronic data files.

F. Sample Size

Up to 500 participants (250 SCI, and 250 control subjects) will be recruited to participate in this study at the VAMHS and at the University of Miami. Based on our previous protocols testing spinal cord injured subjects and healthy control subjects, we have added a 25% attrition rate to the number of subjects we plan to enroll in the study.

All participants will be between 18 and 85 years of age. We plan to recruit both veterans and non-veterans.

G. Data analysis is consistent with the study objective

Aim 1: Repeated-measures ANOVA and Tukey post hoc test will be used to assess the effect of TASK (rest, precision grip/wrist flexion, and precision grip/wrist extension) and GROUP (SCI, controls) on physiological measurements.

Aim 2a: Repeated measures ANOVA and Tukey post hoc test will be used to determine the effect of TIME (0,10, 30, 60 min after a single rTMS session), STIMULATION (rTMS, sham rTMS over control brain area) on physiological and behavioral measurements.

Aim 2b: repeated measures of ANOVA and Tukey post hoc analysis will be used to determine effects of GROUP (training + rTMS, training + sham rTMS), TIME (sessions number 1,5,10 and follow up 1,2, and 3 months) on physiological outcomes and motor performance.

H. Privacy and Confidentiality:

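### If Aim 2b training runs past session 10, the planned analysis has no end-of-training level: TIME goes from session 10 to the 1-month follow-up

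*Combined protocol and SAP*

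**What the plan says.** All references are to the combined protocol and SAP.

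- **Course length.** Phase 3, Experiment 2 (Aim 2b): "Training will be complete in approximately 15 sessions over approximately 3 weeks".
- **Numbered assessments.** Plan for assessment of long-term effects of rTMS: "Physiological and behavioral measurements will be acquired before and after sessions 1,5, and 10".
- **Analysis.** Section G, Aim 2b, is a repeated-measures ANOVA with Tukey post hoc comparisons on physiological outcomes and motor performance. Its factors are GROUP (two arms) and "TIME (sessions number 1,5,10 and follow up 1,2, and 3 months".
- **Possible post-course value.** The Aim 2b text has a heading "Measurements before and after rTMS protocols". It lists physiology, grip performance and function tests but names no session.
- **Follow-up.** The follow-up section says "Follow up measurements will be taken after 1, 2, and 3 months after Phase 3 testing to measure any sustained improvements in hand function". The quality-of-life section dates the same visits differently: "at the follow up visits 1,2, and 3 months after training".
- **Hypothesis.** "precision grip training outcomes will be enhanced by rTMS induced cortical plasticity (aim 2b".

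**The concern.** The assessment list and the TIME factor agree with each other, but both stop at session 10, and the stated course is about half as long again. If the longer course is what participants receive, no analysed time point shows the two arms once training is complete. The Aim 2b hypothesis is about training outcomes, and the difference on completing training is its most direct test.

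The follow-up visits are meant to show whether improvement is sustained, which needs a value at the end of training to compare with. Without one, a between-arm difference at 1 month that is smaller than, equal to or larger than the session-10 difference has no clear reading. Gain in the last sessions and loss after training are merged into one change.

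**Working it through.** **Inputs.** About 15 sessions and about 3 weeks (Experiment 2, Aim 2b); assessments at sessions 1, 5 and 10 (long-term effects paragraph); TIME at sessions 1, 5, 10 and months 1, 2, 3 (section G). The plan states no figure of its own on this point, so there is none to reproduce.

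**1. Share of training after the last analysed in-training value**, (N − 10)/N:

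- N = 15: 5/15 = 33%
- N = 13: 3/13 = 23%
- N = 17: 7/17 = 41%

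The range 13 to 17 is an assumed reading of the word approximately.

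**2. Gap between the two adjacent analysed levels.** At 15/3 = 5 sessions per week, sessions 11 to 15 take about 7 days. Even spacing and a 30-day month are assumed.

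- Follow-up counted from the last training session: 7 + 30 = about 37 days. With 13 to 17 sessions over 2.5 to 3.5 weeks (assumed) and a 30.4-day month, the gap is about 4.9 to 5.8 weeks.
- Follow-up counted from Phase 3 testing, if that means session 10: about 30 days.

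The two follow-up statements do not settle which applies.

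**3. What can be estimated.** Let D10 be the between-arm difference at session 10, g its change from session 10 to the end of training, and d its change from there to 1 month. Then D1m = D10 + g + d. Only D10 and D1m are analysed, so only the sum g + d is estimable. Equal differences at both times fit no change at all, or any late gain g followed by an equal loss. The end-of-training difference, D10 + g, is not estimated.

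**4. Which reading to use at the end.** Section G has Aim 2a measure effects at "TIME (0,10, 30, 60 min after a single rTMS session", so the plan itself expects that there may be an acute after-effect. Suppose a reading taken just after the last stimulation carries such a between-arm effect, a. Follow-up minus that reading gives d − a rather than d, and any acute effect that has worn off is counted as lost training gain. A before-session reading at the final session avoids most of this, although it omits what the final session itself adds.

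**5. Multiplicity from one added level.** Section G does not say whether the before-session reading, the after-session reading or both enter TIME. Two-sided 5% and large degrees of freedom are assumed for the Tukey values.

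| TIME levels now | Levels after | Pairwise comparisons | Tukey critical value | Rise |
|---|---|---|---|---|
| 6 (one reading per session) | 7 | 15 to 21 | 2.85 to 2.95 | 3.5% |
| 9 (both readings: 3 × 2 + 3) | 10 | 36 to 45 | 3.10 to 3.16 | 2.0% |

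These values concern time contrasts. The effect on power for the between-arm contrast cannot be computed, because the documents give no effect size, standard deviation, significance level or within-subject correlation.

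**The case against.** The strongest reply is that the documents may contain no missing level at all. The intended course might end at session 10, or the measurements promised before and after the rTMS protocols might already include one after the full course. The hypothesis names no time point, and the arms are still compared at session 10 and three times in follow-up.

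Much of this stands. The documents do not show whether the session count or the assessment list is the intended one, so the firm finding is an unreconciled schedule, and the missing level depends on how it is resolved. The reply does not remove the point, however. The heading on measurements names no session, and section G lists its TIME levels explicitly without a post-course one. Even if such a value is collected, the planned model does not use it.

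Three stronger readings are tempting and are not supported:

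- A reader might infer that Aim 2b cannot be tested or that the follow-up comparisons are invalid. They are valid between-arm comparisons at their own times; only the end-of-training contrast and the split between late gain and decay are lost.
- A reader might contrast Aim 2b with Aim 2a, which has a level at 0 minutes. Aim 2a analyses a single session, so its first reading is both after-session and end-of-intervention. Aim 2b does have after-session readings, at sessions 1, 5 and 10.
- A reader might infer that no end-of-training data exist for any scale. The self-care independence measure and the upper-extremity capability measure are scheduled before and after training sessions. They are outside this point, because the Aim 2b ANOVA covers physiological outcomes and motor performance.

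**Conclusion.** The point holds in conditional form and should be fixed. The stated course of about 15 sessions does not fit an assessment list and TIME factor that both end at session 10. If training does run past session 10, about a third of it (23% to 41% over the assumed 13 to 17 sessions) follows the last analysed in-training value. The between-arm effect at the end of training is then not estimated, and late gain cannot be separated from later decay. The adjacent analysed levels are about 37 or about 30 days apart, depending on where follow-up starts. The existence of the gap rests on none of the spacing or multiplicity assumptions; they affect only its stated size and the cost of repair.

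**What to change.** 1. Reconcile four places: the course length in Experiment 2, the heading on measurements before and after the rTMS protocols, the paragraph on sessions 1, 5 and 10, and the Aim 2b entry in section G. They should agree on the session count and assessment times. Give follow-up one starting point in both places that mention it.
2. If training ends at session 10, no new level is needed.
3. If it continues past session 10, add an end-of-training level to the Aim 2b TIME factor. Use the post-course value if it is already taken; otherwise take the existing battery at the final scheduled session.
4. State whether before-session or after-session readings enter TIME, and use the same kind at every session.
5. For sustained improvement, compare follow-up with a reading not taken just after stimulation, for example the before-session reading at the final session. Report this beside the comparison with baseline.
6. Analyse with a mixed model for repeated measures. Participants without the new level then stay in at their other levels, whereas conventional repeated-measures ANOVA would drop them.

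**Cost.** A few sentences of text, and at most one or two existing batteries at an existing visit. Training takes about 1 hour. A follow-up session is put at about 1 hour, although its test list omits range of motion and electrical perceptual threshold. One battery therefore makes a visit of about 1 + 1 = 2 hours, and two make about 1 + 2 = 3 hours, the top of the stated 1 to 3 hours. The Tukey critical value for time contrasts rises by about 2% to 3.5%. If the value has to be newly collected late in the study, the end-of-training contrast will rest only on participants still to finish training. The documents do not allow that share to be determined. If a post-course value already exists, this loss does not arise.
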